Medication will not be increased above 600mg/day at this visit. However, if medication adjustments are still needed, an additional blood draw for a serum lithium level may be scheduled with Exam One, with an additional blood draw kit shipped to the participant in advance, OR the participant may be scheduled to complete the visit in clinic.

The following assessments will be completed at the week 10 visit:

- Concomitant Medications
- CGI Behavior (CGI-S, CGI-C)
- CGI Global (CGI-S, CGI-C)
- NPI
- Stereotypic and ritualistic behaviors
- TESS
- Medication compliance (the study partner will be asked to count on camera the number of pills remaining in the bottle they used for the first two weeks to ensure correct dosing. 14 pills should remain in the 2nd bottle if the medication has been taken for 14 days at 450mg/day).

Completed by ExamOne (IF NECESSARY):

- Vital signs
- Serum lithium level
- Safety labs

The week 10 visit is estimated to take 50-60 minutes on average.

Color-codes	
Coordinator	
Physician	
Time	Assessment
10 minutes	TESS, Concomitant Meds, CGI, with
	Patient and Caregiver.
30 minutes	NPI with Caregiver
10 minutes	Medication compliance review

Vital signs and blood draw will be scheduled separately and completed by the Exam One mobile phlebotomy team, who will ship samples directly to the CALM lab for processing.

Week 12 Visit

At CUMC, unblinding by the study physician will occur after all week 12 measures and procedures have been completed.

The following assessments will be completed at the week 12 visit:

- Concomitant Medications
- CDR
- CGI Behavior (CGI-S, CGI-C)
- CGI Global (CGI-S, CGI-C)
- NPI
- Stereotypic and ritualistic behaviors
- TESS
- Zarit Caregiver Burden Interview
- Vital signs
- blood specimens collected
- ECG
- protocol exit form
- Medication compliance: kit collection. An additional 4 bottles (128 pills) should have been used since the week 8 visit if the bottle if the medication has been taken for 28 days at 600mg/day).

Blinding: Lithium/sham levels procedures

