Upon receipt of the completed serum lithium/sham lithium levels form, the study coordinator will contact the study physician and report: the sham/real lithium level, current daily dose, and study interval. Based on this information, as well as observed tolerability and side effects, the study physician will choose to change the patient's dosage or continue with current dosage. The study coordinator will then call the patient's caregiver to inform them of the dosing change or lack thereof. The study coordinator will log all of this information on the lithium/sham level log located in the front of the patient's research chart.

If there are unusual circumstances pertaining to dosage, such as a patient having skipped a dose the day before the blood draw, provide as much relevant information as needed to the unblinded physician so they may generate the most realistic sham level. Study coordinators and physicians should instruct caregivers to avoid administering study medication to a patient the same morning of a blood draw. We are targeting trough serum lithium levels for consistent measurement. If lithium is administered the same morning as a blood draw, the serum lithium level is likely to be artificially high and exceed our target therapeutic levels for this protocol. Caregivers can be instructed to give the lithium dose after the study visit.

Breaking the Blind and Open Treatment

Once all week 12 measures are completed, the study physician will break the blind with the participant and the study partner. The unblinding information is contained in an envelope provided by the research pharmacy, which must be requested and collected prior to the week 12 visit.

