The study physician will review outcome measures and results based on the first 10 weeks of the study, which will be compiled in Excel by the study coordinator before the visit (using the template "Exit Summary" excel document in dopamine>Lithium in FTD>Exit Summaries). The physician will then discuss the possibility of whether to continue the dose of lithium, if the participant was an active responder, or whether to begin a low dose of lithium if the participant was on placebo. If the study physician is not the primary physician for the participant, this decision must be discussed with the referring physician, to whom the study physician may make a recommendation. When referring to outside physicians, it is important to thoroughly inform them of the plan for lithium treatment and the target therapeutic levels for this population. The study coordinator is expected to remain blinded even after the participant completes the trial.

Adverse Events and Protocol Deviations

Adverse events and serious adverse events will be carefully monitored, recorded, and reported in this study. An adverse event (AE) is an unexpected medical occurrence or worsening of symptoms, which does not necessarily have a causal relationship with study treatment. Study physicians should monitor gait disturbances or tremor of at least moderate intensity as well as falls in particular for this study. A serious adverse event (SAE) is a medically serious event, any event requiring hospitalization, and death.

Each patient that has an AE or SAE reported will have an AE log filed in their research chart. Both AE and SAE are to be recorded on the AE log version date 07/18/2016. AE logs are to-data forms for this study. Hardcopy AE forms are rewritten each time new information about the event is

made available, with all revisions kept in paper research charts. However, the database AE form will only contain information reflecting the final resolved event or last recorded information once the patient has left the protocol. Information regarding the treatment provided, outcome, and presumed relationship to study drug will be updated as new information becomes available. Site PIs will sign the bottom of the AE logs for their own site once the patient has exited the protocol.

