5. If a patient cannot swallow the pills: If a patient is having difficulty swallowing the study medication capsules, a study physician can let the caregiver know that the lithium/placebo capsule can be opened and dissolved in applesauce or milk products such as yogurt. The NYSPI pharmacy has approved this procedure with these foods. Do not instruct caregivers to use any other foods without discussing with the lead site. The contents of the active and inactive capsules cannot be distinguished from each other when opened. Caregivers should be instructed to empty as much of the contents of the capsules into a small amount of food (1 tablespoon) and then stir the contents in before administering it to the patient. If this deviation from the protocol does occur, it will be filed as a protocol deviation for that patient.

Visit Checklists

These are item-by-item instructions for reference immediately before/during/after visits. Please refer to earlier sections of the manual for more details.

Screening / Baseline

Pre-visit:

- □ Complete instructions under "Scheduling Visits" section of manual
- Enter subject ID, date, and coordinator/physician initials on page 37 of the "Screening-Baseline INPERSON Packet" (dopamine>Lithium in FTD>Visit Instruments>In Person) & print double-sided. Also print visit schedule.
- Separate into the consent forms, clinician forms (which can be placed in a blue folder), and coordinator forms (kept however you like)
- □ Add paper MMSE, MDRS, and MDRS cards, response sheets (for FBI & Zarit), and copy of consent to coordinator materials
- Prepare & label blood tubes (1 red, 1 gold, 1 purple), petty cash + receipt booklet (\$20/visit hr payment + \$40 transportation payment if applicable)
- Add print names to consent forms where appropriate and mark signature lines with colored post-its (different color for each signer). Note that a study physician must be the "person obtaining consent". It is useful to clip the participant consent not staple so you can easily make photocopies once signed (one for the participant, one for Irving).
- Fill in as much demographic information as you can based on past research / clinical chart. If you are unsure of the accuracy of something, use pencil and confirm at visit.

During visit:

- Conduct consent. Arrange for the independent assessor of capacity to be present either during or immediately following the presentation of consent information. Give them all necessary forms.

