- Confirm in-person date & directions with participant, confirm room booking with CRR, confirm event on RA/physician calendars. Remind participant to bring in used study drug kit & all remaining pills. Remind study partner not to give medication dose morning of visit.
- Email NYSPI pharmacy ahead of time to request the Unblinding Envelope; pick this up from the NYSPI pharmacy.
- Prepare a summary of the participant's trajectory through the trial (dopamine>Lithium in FTD> Exit Summaries > TEMPLATE)
- Enter subject ID, date, and coordinator/physician initials on page 1 of the "Week 12 INPERSON Packet" (dopamine>Lithium in FTD>Visit Instruments>In Person), print doublesided. Also prepare and print visit schedule.
- □ Separate into the Clinician forms which can be placed in a blue folder (INCLUDING the unblinding envelope & exit summary) and coordinator forms

- Add paper MDRS and MDRS cards, laminated response option sheets (for FBI & Zarit) to coordinator materials
- Prepare & label blood tubes (1 red, 1 gold, 1 purple) & petty cash + receipt booklet (\$20/visit hr payment, including past virtual visits, + \$40 transportation payment if applicable)

During visit:

- Collect study drug kit
- □ Complete MDRS with patient. Study partner should sit in waiting room or affirm that they will not aid the participant if they stay in the room.
- Complete blood draw in the phlebotomy room ([name] or [name] will perform this). Collect the purple and gold tubes in a biohazard bag (provided by CRR) along with the CALM requisition form. Collect the red tube in a biohazard bag with the Biomarkers Core Laboratory requisition form
 - Drop the Biomarkers Sample in the Biomarkers Core Laboratory (PH10-104): walk past the reception area to the opposite side of the hall from the clinical rooms & through the double doors. On your right several doors in, you will see the entrance to a large lab space with many cubicles. At the entryway, there is a dropoff bin. This must be done before 3:30pm.
 - Then go to the 15th floor to drop off the CALM sample (drop-off bin in room 15-401 in P&S building, down the blue and white hallway)

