- □ When you return, obtain the ECG machine from the phlebotomy room and a gown from the closet (in rooms 2&4) or drawer under the exam table (rooms 3&5). Close the door blinds and draw the curtain by the exam bed. Have the participant change into the gown with their top clothes removed and the gown tied with the opening in front. Lie the participant down on the exam bed and then place the leads on the sternum and below the ribs and connect the ECG machine as trained. If you are not trained, [name], [name], or the study physician may complete the ECG.
- Once the participant is dressed and the ECG machine is retuned, you may EITHER 1) complete the NPI, FBI, and Zarit with the caregiver (preferred) or 2) move on and schedule a time within 3 days to complete these by phone or zoom. If completing in person, it is helpful to provide the response options (printed in a laminated sheet), and if completing virtually, you may email these to the caregiver in advance.
- □ Pay the study partner (\$20/visit hour, including from virtual visits + \$40 for transportation if relevant) and complete/sign a petty cash receipt.
- The clinician portion of the visit should be conducted LAST and will include the unblinding & planning for future care. Note that the study RA should remain blinded even after the participant completes the trial, so it is recommended for them to pay and say goodbye to the participant before the clinician visit, to avoid being accidentally unblinded.

Post-visit:

- Obtain any missing signatures
- □ Score cognitive testing & caregiver forms
- □ Check CALM website for posting of testing results
 - o sac-cu.org on internet explorer-- download "detailed results"
 - Copy the results into the "Safety Labs Template" file in dopamine>Lithium in FTD>Biological Samples, convert the results to numbers in excel (out of range results will highlight in pink), & print
- □ Obtain physician signature on lab results & ECG
- □ Count remaining pills & confirm with expected count. Once done, drop kit off at the NYSPI pharmacy for destruction.
- □ Enter data on REDCap
- Complete Serum-Sham Lithium level form, as described under Weeks 6/8.

Statistical Procedures and Data Analysis.

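### The week-12 checklist allows the caregiver's NPI to be taken up to 3 days after a visit that ends with unblinding, against the manual's own rule that all week-12 measures come first

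*Combined protocol and SAP*

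**What the plan says.** Two sections of the manual set the order. Week 12 Visit states: "At CUMC, unblinding by the study physician will occur after all week 12 measures and procedures have been completed". The NPI and the Zarit interview are on that section's list of measures. Breaking the Blind and Open Treatment states: "Once all week 12 measures are completed, the study physician will break the blind with the participant and the study partner". The study partner is the person who answers the NPI.

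The week-12 part of Visit Checklists gives the working steps. After the ECG, staff have two options with the caregiver: "complete the NPI, FBI, and Zarit with the caregiver (preferred) or 2) move on and schedule a time within 3 days to complete these" remotely. The next steps are payment and then the clinician: "The clinician portion of the visit should be conducted LAST and will include the unblinding & planning for future care".

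Three other details bear on how this would run:

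- The pre-visit steps put forms in a clinician folder, "INCLUDING the unblinding envelope & exit summary", so the means of unblinding is in the room.
- The exit discussion does not need the week-12 scores: "The study physician will review outcome measures and results based on the first 10 weeks of the study".
- The introduction to the checklists sends the reader back to the body of the manual: "Please refer to earlier sections of the manual for more details".

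Under Statistical Procedures and Data Analysis, the primary outcome is the NPI agitation/aggression domain score (0 to 12), the arms are contrasted at t=12, and the secondary responder definition uses an NPI core score together with the CGI-C.

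**The concern.** The rule in the body of the manual is sound. The difficulty is that the checklist opens an exception for the caregiver interviews without carrying the rule along. Under the deferred option, the listed steps end the visit with unblinding and leave the NPI for a later call.

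The NPI is a subjective report. An informant who has just been told the assignment, and has discussed with the physician whether lithium should be continued or started, may rate agitation differently according to that knowledge. The affected score is the week-12 value of the primary outcome, and it also feeds the NPI part of the week-12 responder status. The analysis sections contain no step that would identify such ratings or set them aside.

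**Working it through.** **1. The texts side by side**

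| Place | Order of week-12 NPI and unblinding |
|---|---|
| Week 12 Visit | All measures first, NPI listed |
| Breaking the Blind and Open Treatment | All measures first; study partner is then told |
| Checklist, week 12, option 1 | NPI in person, then clinician portion: consistent |
| Checklist, week 12, option 2 | NPI within 3 days; clinician portion with unblinding still closes this visit; no hold stated |
| Checklist, week 12, post-visit | No later unblinding step |
| Checklist, baseline | Same 3-day deferral, but the visit simply ends and there is no unblinding |

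The only blinding precaution in the week-12 checklist protects the research assistant, not the informant. Option 2 can be reconciled with the rule only if staff postpone the unblinding on their own initiative.

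**2. Illustration of size (assumed values)**

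The documents give no deferral share, rating shift, SD or correlation, so there is no stated figure to reproduce. From the documents: visits t = 0, 2, ..., 12 (7 points), the random-intercept model with group, time and group x time, and 48 completers, taken as 24 per arm. Assumed: SD 3 points, within-person correlation 0.5, no true effect, the same deferral share in both arms, and a net between-arm shift among deferred ratings of 1 to 2 points.

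- The mean of t is 6 and the sum of squares about it is 36+16+4+0+4+16+36 = 112.
- Weight of the week-12 score in the fitted t=12 value: 1/7 + 36/112 = 0.464. Weight in the slope: 6/112 = 0.0536.
- Contrast SE = sqrt[(2/24) x (0.5 + 0.5 x 0.464)] = 0.247 SD, so the 95% half-width is 1.96 x 0.247 = 0.484 SD.
- Slope SE = sqrt[(2/24) x 0.5/112] = 0.0193 SD per week.
- Bias of the contrast in SD = 0.464 x share x shift/SD. Example at 25% and 2 points: 0.464 x 0.25 x 2/3 = 0.077.
- Two-sided type I error uses the normal approximation with bias/SE as the offset. In the example: 0.077/0.247 = 0.31, giving 6.1%.

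| Deferred | Bias, shift 1 to 2 (SD) | Share of CI half-width | Type I error, contrast | Type I error, group x time |
|---|---|---|---|---|
| 10% | 0.015 to 0.031 | 3 to 6% | 5.0 to 5.2% | 5.1 to 5.4% |
| 25% | 0.039 to 0.077 | 8 to 16% | 5.3 to 6.1% | 5.6 to 7.5% |
| 50% | 0.077 to 0.155 | 16 to 32% | 6.1 to 9.6% | 7.5 to 15.2% |

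**3. Sensitivity at 25% deferral, shifts of 1 to 2 points**

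- SD 2 to 4: bias 0.03 to 0.12 SD; type I error 5.2 to 7.6% (contrast) and 5.3 to 10.7% (group x time).
- Correlation 0.3 to 0.7 with SD 3: 5.2 to 6.3% and 5.4 to 9.2%.
- A 2-point shift is 2/3 = 0.67 SD, inside the 0.58 to 0.83 range that the Power Analysis gives as detectable. It is an upper illustration.

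**The case against.** The strongest reply is that this is an omission and not a contradiction. The rule is stated twice, the checklist never orders unblinding ahead of a deferred NPI, and its introduction points back to the fuller sections. Staff who take option 2 and hold the blind comply with everything. The checklist speaks mainly to the coordinator, whereas the physician who breaks the blind has the rule in the sections on that act. The checklist also wants the coordinator kept blind after the trial, and a later call to an unblinded caregiver would work against that. In-person completion is marked as preferred. The printed visit schedule and the week-12 packet are not reproduced and could fix the order. Finally, every input to the size calculation is assumed.

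Much of this stands. The body of the manual should be read as governing, nothing shows that the wrong order ever occurred, and the numbers are illustrative only. What remains is that the checklist is written as item-by-item instructions for use around the visit. Its steps under option 2, taken in sequence, end in unblinding with the NPI outstanding, and the cross-reference is general. A safeguard for the primary outcome should be stated where the exception to the usual sequence is granted.

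**Conclusion.** The point holds. The checklist is not reconciled with the two sections that govern unblinding, and its deferred route permits an informant who knows the arm to supply the week-12 primary outcome. That is certain from the text. The consequence is not quantifiable from the documents: it is negligible if deferral is rare, and under the assumed values it reaches 0.15 SD only with half the ratings deferred and a 2-point net shift. The Power Analysis makes effect sizes with 95% confidence intervals the main result of this pilot, so bias in the estimate matters more here than the modest change in type I error. The manual should be corrected, and the existing records should be checked for the order of NPI and unblinding.

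**What to change.** - **Checklist.** State that the NPI, FBI and Zarit are completed before the clinician portion that unblinds. If they are deferred, state that the blind is not broken with the participant or the study partner until they are done. State that the same order applies if unblinding takes place at an early-termination visit, since Alternate Scenarios gives that visit all the week-12 measures.
- **Records.** If not already captured, record the date and time of the week-12 NPI and of unblinding. The forms are not reproduced, so these fields may exist.
- **Analysis, only if needed.** If any week-12 NPI was taken after unblinding, repeat the primary model without those ratings, and state that this assumes deferral is unrelated to outcome given the other data in the model.

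The cost is one sentence and at most two fields. In the illustration, dropping deferred ratings raises the contrast SE from 0.247 to 0.253 SD at 25% deferral (2%) and to 0.260 SD at 50% (5%). When the forms are deferred, unblinding and the discussion that follows come up to about 3 days later. By then the visit has already included the step "Collect study drug kit", so this interval should be acknowledged when the sections are reconciled. Completing the forms in person before unblinding, which the checklist already prefers, avoids the delay.

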 - **b.** Available times will be shown for each open date. Draws must be scheduled more than two days in advance. Draws should be scheduled for mornings Mondays through Thursdays.
 - **c**. Click the stethoscope
- 9. The mobile phlebotomist will confirm the visit with the participant 24 hours in advance. Even if they do not receive a response, they will still go to the scheduled appointment.

To view orders:

- 1. Once an order has been created, you can view it in the "Order Center" tab.
- 2. "Paramedical Examination Order" will show the order status and number
- **3.** "Office details" will show the contact information for the office out of which assigned the phlebotomist is based. If you need to reschedule the visit, use this contact information (and you may also contact [name]).
- 4. "Order Services" will show the date/time of the scheduled order
- 5. "Freight #" will show the fedex tracking number once the order has been shipped
- 6. "Status messages" will describe any participant contact

Randomization

Randomization is initiated once it is determined that a patient satisfies all of the inclusion and none of the exclusion criteria. This means that a study drug order form should not be submitted to the pharmacy until all screening visit lab results have been reviewed by a study physician.

Within the study drug order form, the IRB# field should be filled as 7310. For the drug name, strength, dosage form, and Quantity fields, both should be filled as 1 Lithium 150 mg/placebo kit. The Study Week/Visit/Phase field should be filled as Week 0.

Randomization is not officially completed until the medication has been shipped to and received by the participant. If a study drug order form has been submitted and a drug ID has been generated but the patient will not be officially randomized, the randomization order can be canceled by completing the bottom portion of the study drug order form and re-submitting it to the NYSPI pharmacy. If the randomization order is canceled, the drug ID will be made available to the next patient. Once a patient has been officially randomized at baseline, their drug ID cannot be used for any other patient under any circumstances.

Randomization Procedures:

When a new patient enrolls in the study, research coordinator (R.C.) will send a **study drug order form** via email to the NYSPI pharmacy.

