Outcome measures and covariates. Primary outcome: agitation/aggression score (domain score on the Neuropsychiatric Inventory (NPI), continuous measure from 0-12, longitudinal); Secondary outcome: response (dichotomous, based on 30% decrease in NPI core score (sum of domains for motor activity and agitation/aggression) plus a CGI-C score of much improved or very much improved, longitudinal); Exploratory outcome motor activity score on the NPI. Covariates/Predictor variables: 1) demographic characteristics (e.g., gender, race, age); 2) baseline measures of the corresponding outcomes. Other Measures:1) tolerability, as measured by emergent side effects (TESS scores and adverse events) over the course of the 12 week trial; 2) brain derived neurotrophic factor (BDNF) serum levels.

Sample size and randomization: The randomization will be carried out by the statistician and implemented by the pharmacist, who are both otherwise independent of the research team. The randomization sequences will be balanced in blocks of random size to prevent clinicians from guessing what the next patient's treatment might be.

Modeling longitudinal data and testing hypotheses. Modeling longitudinal data and testing hypotheses. All tests will be two-sided; α =0.05; intent-to-treat with data included for all patients with ≥1 post-baseline assessment. We will use generalized linear mixed models (GLMMs; SAS PROC GLIMMIX) for longitudinal data to evaluate study aims. Models will include fixed effects for treatment group, time, group x time interaction, and any baseline covariates found to be unbalanced despite randomization. Prior to analysis, we will examine all variables at all time points for outliers and inconsistencies and examine their distributions.⁴¹⁻⁴³

Primary hypothesis: *Lithium will significantly reduce agitation/aggression as compared to placebo.*

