The following linear mixed effects model will be used: $Y_{ij} = \beta 0 + \beta 1 I T R T + \beta 2t + \beta 3t^* I T R T + \beta 4X_i + \beta 4X_i$ bi + $\epsilon i j$ where Yij is the agitation/aggression score for the *i*th subject at *t*week, *t* =0, 2,...,12, *yi0* is agitation/aggression at baseline, *liTRT* is the indicator variable for randomized condition (placebo vs. lithium), an indicator of recruitment site (Columbia University Medical Center and Johns Hopkins School of Medicine), and any baseline covariates exhibiting imbalance after randomization, bi is a random intercept to account for repeated measures across time within the patient, and $\epsilon i j$ is a random error term. Significant interaction $t^* liTRT$ indicates that the changes in agitation/aggression in each treatment group is different over time (which corresponds to rejecting the null hypothesis that β 3= 0). The effect of time will be estimated for each group separately and the groups will be compared (using contrast) at the last time point t=12. Secondary hypothesis: Lithium will have greater proportion of responders compared to placebo. We will test whether the probability of response by end of active treatment differs significantly in the lithium and placebo groups by a chi-square test. In addition, we will test whether change in the probability of response differs across treatment groups by longitudinal analysis. We will use the generalized linear mixed effects model: logit(Yij) = $\beta 0 + \beta 1$ liTRT+ $\beta 2t$ + $\beta 3t^{*}$ /*iTRT*+ $\beta 4Xi$ + *bi* + ϵij where Yij is the a binary variable indicating response for the *i*th subject at t week, t = 2, 4, ..., 12. We will first test significance of the treatment effect by testing the group by time interaction.

Exploratory Hypothesis. Lithium will significantly reduce repetitive behaviors as compared to placebo. We will use the same model in the analyses for the primary hypothesis where Yij is the motor activity score for the *i*th subject at *t* week, *t* =0, 2,...,12.

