Tolerability: We will assess the tolerability of low dose lithium by assessing emergent side effects over the course of the 12-week trial on lithium compared to placebo. We will compute descriptive statistics of tolerability measures in each treatment group and provide both point estimates and their confidence intervals. We will test whether the change in TESS score from baseline to week 12 differs significantly in the lithium and placebo arms by a t-test.

Biomarker Hypothesis. Increases in BDNF serum levels will be associated with decreases in agitation/aggression and repetitive behaviors. The relationship between change in BDNF serum levels (defined as baseline minus endpoint of active treatment) and the changes in agitation/aggression score and motor activity score (defined as baseline minus treatment endpoint) will be tested using correlation analyses.

Power Analysis. Given the proof-of-concept nature of this study as a pilot, effect sizes with 95% confidence intervals rather than statistical significance testing will be the primary results of interest. The overarching aim is to demonstrate feasibility for conducting a larger trial which would then be used to adequately test efficacy.³³ Nevertheless, we provide some guidance regarding the statistical power available for testing differences between treatments. With n=60 patients randomized (30 to lithium, 30 to placebo) we conservatively examine power below assuming attrition will be 20% (i.e. 48 completers) though our past studies have all had attrition <20% and all available longitudinal data will be used for all individuals regardless of whether they complete the 12 weeks. For the primary outcome of agitation/aggression score measured by the NPI, we will have 80% power to detect a medium to large treatment effect size of 0.58-0.83 with the range depending on the within person correlation over time. Additionally, for responder status, we will have >80% power to detect a difference between, for example, a 15% response rate and a 50% response rate at 12 weeks. Differences among other exploratory outcomes and tolerability measures will be detectable with similar power.

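### The set called intent-to-treat is a modified one, and the secondary responder chi-square has no all-randomised denominator or rule for unknown response, so early failures can leave that comparison

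*Combined protocol and SAP*

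**What the plan says.** Under Statistical Procedures and Data Analysis, the paragraph on modelling longitudinal data sets the analysis population: "intent-to-treat with data included for all patients with ≥1 post-baseline assessment".

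The secondary hypothesis paragraph then says of the responder outcome: "We will test whether the probability of response by end of active treatment differs significantly", by a chi-square test with a longitudinal logistic model alongside. It names no denominator for the chi-square and no rule for a patient whose response is unknown.

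Other places that bear on the point:

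- **Randomization:** "Randomization is not officially completed until the medication has been shipped to and received by the participant". A patient therefore counts as randomised once the kit has arrived.
- **Introduction and Alternate Scenarios:** dropouts are to be assessed when they exit. The early termination visit repeats the week 12 measures and is filed in the database jointly as week 12 or early termination. After a medical interruption that cannot be resolved, the visit is asked for only where it can be arranged.
- **Power Analysis:** "all available longitudinal data will be used for all individuals regardless of whether they complete the 12 weeks". Effect sizes with 95% confidence intervals are named as the main results.

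Nowhere are leavers counted as non-responders, and no analysis of all randomised patients is planned.

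**The concern.** The requirement of one post-baseline assessment is a filter applied after drug is in hand. Early intolerance, which lithium can cause, is one route to failing it. The Introduction itself mentions dropout from lithium toxicity, although at higher levels. The arms could therefore lose different patients.

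A mixed model can absorb missed visits, but a two-by-two table cannot. As written, a leaver's place in the responder table depends on circumstance:

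1. Left before week 2 with no exit visit: removed by the stated rule.
2. Left at any time and attended an exit visit: in the set, with a value that can be scored.
3. Left after week 2 with no exit visit: in the set, but with no defined end-of-treatment response.

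A patient who stops because the drug was not tolerated or did not help is a treatment failure. Removing such patients raises the observed response rate in the arm that loses more of them. The trial is meant to give an effect size for planning a larger study, so a shifted difference matters even where the p-value stays on the same side of 0.05.

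**Working it through.** **Inputs from the documents.** 60 randomised, 30 per arm; 20% attrition, leaving 48 completers (24 per arm if even); responder example of "a 15% response rate and a 50% response rate at 12 weeks" with power above 80%; "All tests will be two-sided; α =0.05". All are in the Power Analysis and modelling paragraphs.

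**Assumed, because the documents do not say.** The number leaving with no post-baseline assessment (0 to 4 in one arm is shown below) and the responder counts.

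**Step 1: the plan's own responder power.** Normal approximation to the uncorrected chi-square:

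power = Φ[(|p1 − p2| − 1.96·s0) / s1], with s0 = √(p̄(1 − p̄)·2/n) and s1 = √(p1(1 − p1)/n + p2(1 − p2)/n).

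- n = 30 per arm: p̄ = 0.325, s0 = 0.1209, s1 = 0.1122. Power = Φ[(0.35 − 0.2370)/0.1122] = 84.3%.
- n = 24 per arm: s0 = 0.1352, s1 = 0.1254. Power = Φ[(0.35 − 0.2650)/0.1254] = 75.1%. An unpooled variance gives 79.7%.

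The stated figure holds on all 60. On 48 it is reached only approximately, and only with the unpooled variance.

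**Step 2: effect of the stated rule on the responder table.** Start from 10/30 lithium and 4/30 placebo and drop early failures. Uncorrected Pearson chi-square; Wald 95% interval for the difference.

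| Excluded (lithium, placebo) | Table | Difference, points | 95% CI | p |
|---|---|---|---|---|
| 0, 0 | 10/30 v 4/30 | 33.3 − 13.3 = 20.0 | −0.8 to 40.8 | 0.067 |
| 2, 0 | 10/28 v 4/30 | 35.7 − 13.3 = 22.4 | 0.9 to 43.9 | 0.047 |
| 4, 0 | 10/26 v 4/30 | 38.5 − 13.3 = 25.1 | 2.8 to 47.4 | 0.030 |
| 2, 2 | 10/28 v 4/28 | 35.7 − 14.3 = 21.4 | −0.5 to 43.4 | 0.064 |
| 0, 2 | 10/30 v 4/28 | 33.3 − 14.3 = 19.0 | −2.2 to 40.3 | 0.090 |

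The shift comes from imbalance and goes against whichever arm loses fewer failures.

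**Step 3: false positives when there is no true difference.** Let 30% respond in both arms over all randomised. Excluding k lithium failures makes the assessed lithium rate 0.30 × 30/(30 − k). With k = 0, 2, 3, 4 and 6, the rejection rate is 4.9%, 5.3%, 6.6%, 6.7% and 10.2%. With k = 2 the spurious difference is 32.1 − 30.0 = 2.1 points; with k = 6 it is 7.5. The last case puts the whole of the plan's 20% attrition before any assessment, in one arm only.

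**Step 4: power after the fix.** If 15% and 50% are rates over all 30 per arm, power stays at 84.3%. If they are rates among 24 assessed per arm and all 6 leavers per arm count as failures, they become 0.15 × 24/30 = 12% and 0.50 × 24/30 = 40%. The difference falls from 35 to 28 points, and power at 30 per arm is 70.6%.

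**Step 5: primary outcome.** A check of the random-intercept model used an assumed SD of 3 and within-patient correlation of 0.3 to 0.7, and added 3 baseline-only lithium patients to 27 v 30 complete ones. The week-12 contrast moved by less than 0.1 point on average on the 0–12 scale, centred on zero.

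**The case against.** **The rule should bite rarely.** The first assessment is at week 2, normally by video, with the NPI taken from the caregiver. Dropouts are to be assessed on exit. Patients who stop medication early are to complete the week 12 measures at their next visit, and patients at high risk of leaving are to complete them at once. A patient handled in this way has a post-baseline assessment and stays in. This stands, and it is why the effect is likely to be small. It does not close the gap, because the visit cannot be guaranteed and no rule covers those who miss it.

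**Attrition as a whole is not this rule.** A reader might infer that the requirement discards all of the 20% attrition and turns 12/30 v 4/30 (26.7 points, p = 0.020) into 12/24 v 4/24 (33.3 points, p = 0.014). The text does not support that. Someone who leaves at week 4 or later normally has a post-baseline assessment and remains in the set. That example shows the missing-response rule that the plan leaves open, and end of active treatment could also be read as last available status.

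**The primary result.** A reader might also infer that the primary effect estimates no longer compare the randomised groups. Step 5 does not bear that out: baseline-only patients say almost nothing about change.

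**Kit receipt.** Counting patients as randomised only on receipt might look like a further exclusion related to treatment. It comes before dosing and under blind, and it is a workable definition of the denominator.

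**The remedy is not neutral.** Counting unknown response as failure lowers both rates and can cost power. It would be wrong if it overrode exit-visit data. Both points are accepted and shape the fix.

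**Conclusion.** The concern holds for the secondary responder analysis. The label does not match the set, the chi-square lacks a denominator and a rule for unknown response, and no other part of the plan restores the patients removed. The statement in the Power Analysis about using all available data cannot help a patient who has none after baseline.

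The size rests on assumed counts. With 2 to 4 lithium-only exclusions from 10/30 v 4/30, the difference rises by 2.4 to 5.1 points, enough in that example to move the interval off zero. With two exclusions in each arm it rises by 1.4 points and the interval still includes zero. Bias is possible, and its direction depends on which arm loses more failures. The documents do not show that it will occur or that it will favour lithium, and harm to the primary analysis is not shown. The point is worth correcting before analysis because the correction is cheap, but it does not threaten the trial.

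**What to change.** For the responder chi-square, state in the SAP:

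1. The denominator is every patient randomised as the Randomization section defines it (kit received), by assigned arm.
2. A patient with a week-12 or early-termination assessment is scored from that visit, in line with how the database files it.
3. A patient with neither is a non-responder.
4. The as-observed table, on patients with at least one post-baseline assessment, is a sensitivity analysis. Report leavers by arm and timing beside it.

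For the primary mixed model, either drop the post-baseline requirement or call the set modified intent-to-treat. Dropping it is straightforward if week 0 is an outcome row, as the model's time index says, and the estimate will hardly change. The same paragraph also defines a baseline score, and baseline outcome values are listed among the covariates. The SAP should say which role baseline has, since a week-0 row is uninformative if that same value is also a covariate.

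Cost: SAP wording and one extra table, with no new data. Reported response rates will be slightly lower. If the 15% and 50% planning rates were meant for assessed patients, responder power could fall to about 71% (12% v 40% at 30 per arm); if they were meant for all randomised, it stays at about 84%.
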